6.2 IMPORTANT PROTOCOL DEVIATIONS

Handling of IPDs is included in the DV domain specifications and stored within the TMF in EDMS.

IPDs will not lead to exclusion from analysis sets.

6.3 SUBJECT SETS ANALYSED

The following analysis sets will be defined:

Screened Set

The screened set (SS) includes all patients for whom a signed informed consent is available at the time of final DBL. It will be used only for display of patient disposition.

Randomised Set

The randomised set (RS) includes all screened patients who were randomised in the trial, regardless of whether any study drug was taken. It will be used only for display of patient disposition and IPDs.

Treatment assignment will be as randomised (i.e. planned maintenance treatment).

Treated Set

The treated set (TS) is defined as all randomised patients who received at least one dose of study treatment.

The TS will be used for presentation of demographic/baseline data, concomitant medications/diagnoses, treatment exposure and safety.

Treatment assignment will be according to actual maintenance treatment (see [Section 6.1.3](#)), but certain AE summaries will also consider assignment according to planned (i.e. randomised) maintenance treatment.

It is not expected on the database that the situation in which a patient could be treated without randomisation will exist. Documentation is in place by the Interactive Response Technology (IRT) vendor, which states that, should any patient be given treatment at the site in error without randomisation, such a patient will be subsequently randomised to a treatment which is not incompatible with the one given in error.

Full Analysis Set

The full analysis set (FAS) is defined as all randomised patients who received at least one dose of study treatment and who have analysable data for at least one efficacy endpoint.

In practice, “analysable” is considered to mean an observed baseline and an observed post-baseline value for at least one efficacy endpoint.

The FAS will be used for presentation of demographic/baseline data and for summaries and analysis of efficacy.

Treatment assignment will be as randomised (i.e. planned maintenance treatment), but certain analyses will also consider assignment according to actual maintenance treatment (see [Section 6.1.3](#)).

Pharmacokinetic Set

The pharmacokinetic set (PKS) is defined as all patients in the TS who provide at least one evaluable BI 456906 plasma concentration which was not flagged for exclusion.

The table below summarises the analysis sets and their main intended purpose (specific details on sensitivity analyses, missing data, etc. are included in the relevant analysis section):

Table 6.3: 1 Subject sets analysed

Data type	Analysis set				
	SS	RS	FAS	TS	PKS
Disposition	x	x			
Demographic and baseline characteristics			x	x	
Concomitant diseases and medications				x	
Exposure to study drug				x	
Primary efficacy endpoint			x		
Secondary efficacy endpoints			x		
Further efficacy endpoints			x		
Other efficacy and biomarkers			x		
Adverse events				x	
Vital signs				x	
Laboratory safety data				x	
12-lead ECG				x	
Other safety				x	
Plasma BI 456906 concentration					x

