7.5 DETERMINATION OF SAMPLE SIZE

Sample size evaluation was performed using simulation in R software (version 3.6.1), with 10000 simulations performed for each scenario summarised below.

The sample size calculation was based on the following assumptions:

- An overall significance level of 2.5% (one-sided) for the contrast test of the null hypothesis of flat dose response
- The (monotone) dose response shapes specified in [Section 7.2.2](#)
- A placebo effect size (mean percentage change from baseline in body weight at Week 46) of zero
- A maximum effect size (mean percentage change from baseline in body weight at Week 46) in the highest dose group of -10.0%
- A standard deviation of 7.0% [[R20-0479](#)].

Simulations were also performed to investigate departures from the assumed true maximum effect stated above, as well as for different scenarios for the true nature of the dose response relationship. The probability of success for each of these scenarios is summarised in [Table 7.5: 1](#) below.

A success was defined as meeting all 3 of the following criteria:

1. Null hypothesis of flat dose response was rejected in favour of at least one of the alternative candidate models, and
2. A target dose was selected within the dose range using the following criterion: difference in mean between selected dose and placebo < -9.0%, and
3. Proportion of patients in the highest dose group meeting the responder definition (percentage change in body weight from baseline < -10.0%) was greater than 35%.

Table 7.5: 1 Probability of success with N=70 patients in each treatment group and SD = 7.0%.

| | Probability of success (%) | | | | | | |
|-------------------------|----------------------------|-------------|-------------|--------------------|--------------------|---------------------|-------------|
| | | Linear | Exponential | E _{max} 1 | E _{max} 2 | SigE _{max} | AVERAGE |
| True maximum effect (%) | -9.0 | 48.9 | 48.9 | 48.8 | 49.0 | 65.3 | 52.2 |
| | -9.5 | 67.8 | 68.3 | 69.1 | 67.9 | 79.2 | 70.5 |
| | -10.0 | 82.8 | 83.3 | 83.8 | 83.3 | 89.0 | 84.4 |
| | -10.5 | 92.4 | 92.6 | 93.2 | 92.2 | 95.6 | 93.2 |
| | -11.0 | 97.1 | 97.3 | 97.8 | 96.5 | 98.4 | 97.4 |

A sample size of 70 patients per treatment group gives a probability of success of greater than 80% for all assumed dose response shapes, with the assumed maximum dose effect and standard deviation as stated earlier.

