Further simulations were performed to investigate the sensitivity of the probability of a successful trial outcome (as presented in [Table 7.5: 1](#)) to different possible allocation ratios which might be observed in practice in an analysis which uses actual maintenance dose. It is possible that some patients may not be able to reach the BI 456906 maintenance dose they

were randomised to according to the planned titration steps in [Section 4.1.4](#), and will receive a lower maintenance dose instead. The scenarios investigated consider the possibility of tolerability issues for patients randomized to the highest BI 456906 dose only, and tolerability issues for patients randomized to one of the top two BI 456906 doses.

All other assumptions other than the allocation ratio are unchanged from what is presented in [Table 7.5: 1](#). For each scenario, 10000 simulations were again used. For simplicity, only the average probability of a successful outcome across the different assumptions on functional form (linear, exponential etc.) is presented in [Table 7.5: 2](#) below. The notation “X-X-X-X-X” is used to refer (from left to right) to the number of patients who received maintenance doses of 0 mg (Placebo), 0.6 mg, 2.4 mg, 3.6 mg and 4.8 mg respectively.

Table 7.5: 2 Probability of success for unequal allocation scenarios in an analysis of actual maintenance dose

| Average probability of successful trial outcome (%) | | | | | | |
|---|-------------------------|------|------|-------|-------|-------|
| Unequal Allocation ratio | True maximum effect (%) | | | | | |
| | | -9.0 | -9.5 | -10.0 | -10.5 | -11.0 |
| | 70-70-70-80-60 | 52.0 | 69.4 | 83.5 | 92.4 | 97.2 |
| | 70-70-70-90-50 | 51.7 | 68.7 | 82.7 | 91.8 | 96.6 |
| | 70-70-80-80-50 | 51.5 | 68.6 | 82.4 | 91.6 | 96.7 |
| | 70-70-90-60-60 | 51.6 | 69.7 | 83.7 | 92.4 | 97.0 |
| | 70-70-100-60-50 | 52.0 | 68.6 | 82.2 | 91.3 | 96.6 |

The average probability of success remained above 80% for the assumed maximum dose effect for all unequal allocation scenarios investigated.

8. INFORMED CONSENT, TRIAL RECORDS, DATA PROTECTION, PUBLICATION POLICY, AND ADMINISTRATIVE STRUCTURE

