6.1.3 Actual Maintenance Treatment

According to the rules for escalating and adjusting the BI 456906 dose given in the CTP, it is envisaged that some patients may not receive the planned maintenance treatment according to the randomised treatment group, whilst nevertheless remaining on treatment.

Actual maintenance treatment will therefore be defined for analysis as follows:

- If the actual dose at the start of the maintenance period is known to be less than the planned maintenance dose to which the patient was randomised, then actual maintenance treatment will be defined as this dose at the start of the maintenance period (which is expected to be one of the lower planned maintenance doses).
- If the patient was known to have discontinued treatment during the dose escalation period, actual maintenance treatment will be defined as the next planned maintenance dose up from the last dose which was taken prior to the dose at the time of discontinuation. This is specified in the table below, for all dosing possibilities planned in the CTP. The same rule will be applied irrespective of the reason for discontinuing treatment during the dose escalation period.

Table 6.1.3: 1 Definition of actual maintenance treatment for patients randomised to active BI 456906 maintenance treatment who discontinued treatment during the dose escalation period

Dose at discontinuation / Previous dose	Actual maintenance treatment
0.3 mg / NA	0.6 mg
0.6 mg / 0.3 mg	0.6 mg
0.9 mg / 0.6 mg	2.4 mg
1.2 mg / 0.9 mg	2.4 mg
1.8 mg / 1.2 mg	2.4 mg
2.4 mg / 1.8 mg	2.4 mg
3.0 mg / 2.4 mg	3.6 mg
3.3 mg / 2.4 mg	3.6 mg
3.6 mg / 3.0 mg	3.6 mg
4.2 mg / 3.3 mg	3.6 mg
4.8 mg / 4.2 mg	4.8 mg

- In all other cases, actual maintenance treatment will be defined equal to planned maintenance treatment.
- All patients randomised to placebo maintenance treatment will be assigned to placebo for actual maintenance treatment.

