7.4 PRIMARY ENDPOINT(S)

Descriptive summaries of body weight and percentage change from baseline will be presented over time. These summaries will be produced in each of the following different ways:

- FAS, planned maintenance treatment, all data (i.e. both on-treatment and off-treatment as defined in [Section 6.1.6](#), and irrespective of any anti-obesity medications subsequently introduced for patients who discontinued treatment early)
- FAS, planned maintenance treatment, all data (as above) but censored for any early treatment discontinuation related to the COVID-19 pandemic (either direct COVID-19 infection or other indirect pandemic-related reason)
- FAS, planned maintenance treatment, on-treatment data only
- FAS, actual maintenance treatment, all data censored for COVID-19 related treatment discontinuation
- FAS, actual maintenance treatment, on-treatment data only.

The first descriptive summary above, which uses all available body weight data, will be repeated split at each time point according to whether the contributing data are on- or off-treatment.

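### One descriptive body weight summary by actual maintenance dose credits off-drug Week 46 weights of escalation stoppers to doses they never maintained, so it looks steeper than the randomised comparison

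*SAP*

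**What the plan says.** SAP 6.3 sets the default for efficacy and announces an exception: "Treatment assignment will be as randomised (i.e. planned maintenance treatment), but certain analyses will also consider assignment according to actual maintenance treatment". The operative text is in two other places.

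- SAP 7.4 lists five descriptive summaries of body weight and percentage change. One is "FAS, actual maintenance treatment, all data censored for COVID-19 related treatment discontinuation". It keeps off-treatment weights, except after COVID-19 related stops.
- SAP 6.1.3 states: "If the patient was known to have discontinued treatment during the dose escalation period, actual maintenance treatment will be defined as the next planned maintenance". That sentence goes on to count the step up from the dose before the one at which the patient stopped, and the rule ignores the reason for stopping. Table 6.1.3: 1 spells this out. A stop at 0.9 mg, for example, counts as 2.4 mg. Patients randomised to placebo always stay in placebo.

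SAP 6.1.6 ends the on-treatment period 28 days after the last dose, so the Week 46 weight of an escalation stopper is off-treatment. SAP 7.4 plans a split into on- and off-treatment data only for the first summary, which is by planned treatment.

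Protocol 7.5 discusses an analysis by actual dose for patients who cannot reach the randomised dose "and will receive a lower maintenance dose instead". Those patients do take a maintenance dose.

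**The concern.** A table by actual dose is normally read as response to the dose received. Here a patient randomised to 4.8 mg who stops in week 6 at 0.9 mg, and is weighed at Week 46 after about 40 weeks off drug, counts as a 2.4 mg response. Column membership depends on a post-randomisation outcome, namely how far the patient got through escalation. Poor outcomes move down from the upper doses, while placebo keeps all of its stoppers.

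The trial is meant to describe the shape of the dose response, with 9 points over placebo as the target. SAP 7.4.1 says that the choice of Phase 3 dose will also weigh other relevant information. A table on the primary endpoint that shows the top dose beyond 9 points, when the randomised comparison does not, could colour that choice.

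**Working it through.** **Inputs from the documents.** Protocol 7.5 gives "An overall significance level of 2.5% (one-sided) for the contrast test of the null hypothesis of flat dose response", "A sample size of 70 patients per treatment group gives a probability of success of greater than 80% for all assumed dose response shapes", "A maximum effect size (mean percentage change from baseline in body weight at Week 46) in the highest dose group of -10.0" percent and "A standard deviation of 7.0" percent, with placebo at zero.

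**The plan's own figure.** Simulating the protocol's three-part success rule at a true maximum effect of -10% (10,000 trials per shape) gives an average success probability of 84.6%, against 84.4% in Protocol Table 7.5: 1. The equal-weight contrasts match SAP Table 7.4.1: 1 to three decimals. This confirms the reading of the inputs; the point itself does not depend on it.

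**Where stoppers go.** Applying SAP Table 6.1.3: 1 to the schedule in Protocol Table 4.1.4: 1:

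- 4.8 mg arm: weeks 1-4 to 0.6 mg, weeks 5-12 to 2.4 mg, weeks 13-16 to 3.6 mg; weeks 17-20 stay.
- 3.6 mg arm: weeks 1-4 to 0.6 mg, weeks 5-14 to 2.4 mg; weeks 15-20 stay.
- 2.4 mg arm: weeks 1-4 to 0.6 mg; the rest stay.
- 0.6 mg arm and placebo: all stay.

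With stops spread evenly over 20 weeks, the share moved down is 16/20 = 80%, 14/20 = 70%, 4/20 = 20% and 0%.

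**Assumptions not in the documents.** Escalation stop rates of 10/10/15/20/25% (placebo, 0.6, 2.4, 3.6, 4.8 mg), evenly timed. Stoppers average -2% at Week 46 in every arm, and all are weighed then. There are no maintenance stops and no down-titration. On-drug means are linear, -10 × dose/4.8: 0, -1.25, -5, -7.5, -10.

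**4.8 mg**

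- By randomised arm: 0.75 × (-10) + 0.25 × (-2) = -8.0. Placebo: 0.90 × 0 + 0.10 × (-2) = -0.2. Difference: -7.8.
- By actual dose: 52.5 completers stay, and 17.5 × 0.2 = 3.5 stoppers stay. (52.5 × (-10) + 3.5 × (-2))/56 = -9.5. Difference: -9.3.

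**2.4 mg**

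- By randomised arm: 0.85 × (-5) + 0.15 × (-2) = -4.55. Difference: -4.35.
- By actual dose: 59.5 completers, 8.4 own stoppers, 7 from the 3.6 mg arm and 7 from the 4.8 mg arm. (59.5 × (-5) + 22.4 × (-2))/81.9 = -4.18. Difference: -3.98.

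| Column | Minus placebo, randomised | Minus placebo, actual | Expected n, actual |
|---|---|---|---|
| Placebo | – | – | 70.0 |
| 0.6 mg | -1.13 | -1.20 | 78.4 |
| 2.4 mg | -4.35 | -3.98 | 81.9 |
| 3.6 mg | -6.20 | -6.64 | 63.7 |
| 4.8 mg | -7.80 | -9.30 | 56.0 |

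**Sensitivity.** For the 4.8 mg column, with stop rate s, on-drug mean m and off-drug mean o, the shift is (o - m) × 0.8s(1 - s)/(1 - 0.8s). The placebo column is the same in both displays and cancels.

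- s = 0.25, o = -2: 8 × 0.1875 = 1.5 (the case above)
- s = 0.25, o = -4: 6 × 0.1875 = 1.1 (-8.1 becomes -9.2)
- s = 0.10, o = -2: 8 × 0.0783 = 0.6 (-9.0 becomes -9.6)
- s = 0.10, o = -4: 6 × 0.0783 = 0.5
- s = 0.30, o = -2: 8 × 0.2211 = 1.8
- s = 0.30, o = 0 (full regain): 10 × 0.2211 = 2.2

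**Shape.** Thirty scenarios were run: the five candidate shapes, active-arm stop rates of 5/10/10/15% or 5/15/20/30%, and off-drug means of 0, -2 or -4. The fitted slope by actual dose was steeper than by randomised arm in all 30. It was shallower than the assumed on-drug slope in all 30. For the linear shape with the higher stop rates, the slopes per mg were -1.89 to -1.92 by actual dose, -1.49 to -1.73 by randomised arm and -2.08 on drug. The segment from 2.4 to 4.8 mg alone was steeper than on drug in 22 of 30.

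**The case against.** The strongest reply is that nothing planned depends on this table. It is one of five descriptive summaries, with no contrast, test or model attached. The MMRM, the MCPMod test and the 9-point target in SAP 7.4.1 all use randomised dose. The -9.3 is a subtraction that a reader would have to make. SAP 7.4 also plans the direct comparator (planned treatment, same COVID-19 censoring) and on-treatment summaries by planned and by actual dose, and analysis-set counts are tabulated both ways. All of this stands and limits the point to a supplementary display.

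The size is also uncertain. Stop rates, timing and off-drug means are assumptions, and incomplete Week 46 follow-up would shrink the shift. The change at 2.4 mg, 0.37 points, is under half a standard error (7/√82 = 0.77). That stands too.

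Some stronger readings are tempting but not supported:

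- *The 4.8 mg column keeps almost only tolerators.* Stoppers in weeks 17-20 stay there, as do maintenance stoppers who began on 4.8 mg. The tolerator share is 92% to 98% with 10% to 30% escalation stops and no maintenance stops. It falls to 79% with 30% escalation and 10% maintenance stops.
- *The display overstates the drug's effect.* The -9.3 is smaller than the assumed on-drug -10. It exceeds only the randomised treatment-policy value.
- *SAP 6.1.3 contradicts Protocol 7.5.* The protocol section describes sample-size scenarios and does not define actual dose. The SAP goes further than the case described there, which is not a conflict.

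The reply does not remove the core fault: off-drug weights are shown as responses to maintenance doses that the patients never took, and the one split that would reveal this is not planned for this table.

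**Conclusion.** The point holds for the all-data summary by actual dose in SAP 7.4. Under every assumption tried, it is steeper than the randomised all-data comparison. The 4.8 mg column is shifted by about 1.5 points in the main scenario and by roughly 0.5 to 1.8 points with 10% to 30% stopping at 4.8 mg and off-drug means of -2% or -4%. It reaches 2.2 at 30% if stoppers regain everything. In the main scenario the two displays fall on either side of 9 points (-7.8 and -9.3), so a reader might infer that the target was met. That inference would be wrong, because the target dose comes from the model fitted to randomised dose.

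The direction follows from the rule as long as stoppers lose less weight than patients who stay on drug at the upper doses. The size rests on rates that the documents do not give. SAP 7.4.2 is not in the released text, so no claim is made about modelled analyses by actual dose. This is a cheap improvement to a supplementary table and does not threaten the primary result.

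**What to change.** In the all-data efficacy summary by actual maintenance treatment:

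- Reassign only patients who started maintenance on a lower planned dose, the case Protocol 7.5 describes. Keep escalation stoppers in their randomised arm. In the scenario above, which has no down-titration, this restores -7.8.
- Extend the on/off-treatment split in SAP 7.4 to this summary.
- Show the number of reassigned patients per column and label the table as a non-randomised comparison.

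Alternatively, drop this summary and keep the on-treatment one by actual dose.

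Do not restrict the table to patients who started maintenance, or move stoppers to a separate group. Either would leave only patients who completed escalation in the 4.8 mg column. With the same restriction on placebo, the scenario would read -10.0 - 0 = -10.0, further from the randomised -7.8 than the present -9.3.

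The cost is a few lines of SAP text and one derived variable. The table becomes a mix of randomised and received dose, and efficacy and safety tables will use slightly different definitions of actual dose. A footnote should state both.

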6.5 POOLING OF CENTRES

No analysis will be performed in which centre is included in the statistical model.

Subgroup analysis will be performed by country and region, but no other pooling of centres will be performed.

6.6 HANDLING OF MISSING DATA AND OUTLIERS

Primary efficacy endpoint

Every effort will be made to keep the patient in the trial and taking study treatment, where possible. If the patient discontinues from treatment early, every effort will also be made to capture body weight post-discontinuation up to and including Week 46, or at least a single measurement at Week 46. These data will be used in the treatment policy strategy for handling early treatment discontinuation in the analysis (see [Section 7.4](#) for analysis details), noting also that the protocol permitted home measurement to be used and entered onto the eCRF in these circumstances, if the patient was unable or unwilling to return to site. Nevertheless, there may still be some missing data, even using such a treatment policy strategy for analysis. In the

hypothetical strategy for handling early treatment discontinuation, off-treatment body weight values (as defined in [Section 6.1.6](#)) will not be used and will be handled as if these data were missing.

In both cases, missing data will be handled implicitly by the statistical model (mixed model for repeated measures (MMRM)). This model makes the assumption that the data are missing at random (MAR). Patients who do not have a Week 46 body weight value, but who have earlier post-baseline values, still contribute to this analysis. MAR means that a patient who drops out is assumed to have behaved like a similar patient within the same treatment group (where “similar” means both with regard to baseline covariates in the model and to the observed trajectory of body weight values prior to drop out).

A sensitivity analysis for the hypothetical strategy which does not make the MAR assumption, and which makes a more conservative assumption, is specified in [Section 7.4.2](#).

Sensitivity analyses for the treatment policy strategy which do not use standard MMRM are also expected to be performed. These will be done post-hoc, and they are not described further in this TSAP.

Responder secondary efficacy endpoints

For the responder endpoints derived from percentage change from baseline in body weight at Week 46, analyses will be performed in which the handling of data after early treatment discontinuation and missing data are aligned with the treatment policy and hypothetical strategy approaches for the underlying continuous primary endpoint.

This will be done by performing a multiple imputation (MI) analysis which makes the same MAR assumption as the MMRM used to analyse the primary endpoint. Essentially, missing data will be imputed under the MAR assumption, to give 1000 complete datasets containing body weight values (observed and imputed) for all patients. The responder endpoints at Week 46 will be derived for each patient from the complete data in each of the imputed datasets, each dataset then analysed, and the results combined across the imputed datasets in a way which correctly accounts for the within and between imputation variance. Details of both the multiple imputation procedure and the subsequent analysis are given in [Section 7.5.2](#).

All other efficacy endpoints

No imputations will be performed for any other efficacy endpoint. Where continuous endpoints over time are analysed using a statistical model, this will be MMRM, which implicitly handles missing data using the MAR assumption.

Safety/Other

A completely missing concomitant medication start date will be assumed to mean present at screening. If only the month and year are available for the AE/concomitant medication start date, the first day of the month will be assumed. If only the year is available, then 1st January of that year will be assumed. In the case of AE start dates (only), if the stated imputation would make the AE become pre-treatment when this was not known from the incomplete date, it will be assumed instead that the AE started on the first day of treatment.

If only the month and year are available for date of last administration of study medication, the last day of the month will be assumed.

If only the month and year are available for the date of first administration of study medication, the date of randomisation will be used if they are in the same month. If randomisation was in the month prior to first drug administration, the first day of the month of first administration will be assumed.

PK data

Missing data and outliers of PK data are handled according to BI standards.

